Approximately 15% patients undergoing PCI have HBR and are generally excluded or underrepresented in the DES trials.^{13, 14} These patients will benefit from shorter duration of DAPT. However, contemporary clinical trials are done with newer stent designs (polymer-free)¹³ include older adults with no inclusion criteria that denote HBR¹⁵ or have prespecified subgroup with HBR¹⁶ significantly limiting the generalizability. The decline in the rates of stent thrombosis with newer generation stents coupled with paucity of data to guide clinical decision-making in this high-risk group highlights the importance to develop simple treatment protocols to lower their bleeding risk. Early bleeding hazard with aspirin coupled with time-dependent increase in major bleeding events underscores the need to aggressively deescalate DAPT, albeit not at the expense of heightened ischemic risk. Such reduction in concomitant ischemic events can be achieved with genotype guidance. A post-hoc analyses of TAILOR PCI demonstrated an almost 80% risk reduction for ischemic events with genotype guidance in the first 3 months after PCI, the highest risk period following PCI. Potential advantages of genotype-guided P2Y₁₂ inhibitor therapy in which a large number of patients receive clopidogrel (given an approximate 50% to 70% prevalence of *CYP2C19* noncarriers) and the remainder receive more potent alternative P2Y₁₂ inhibitors is lower cost and lower risk for bleeding for this group as compared with patients receiving either ticagrelor or prasugrel. Furthermore, reduction in ischemic events with newer P2Y12 inhibitors could only be demonstrated among *CYP2C19* loss-of-function (LOF) carriers, underscoring the utility of upfront genetic testing prior to routine DAPT prescription in patients with HBR undergoing PCI. Our specific aims of the present pilot and safety study are:

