Specific Aim 1: Test the hypothesis that clopidogrel monotherapy is safe following successful PCI among 100 consecutive patients with HBR and meeting the inclusion criteria (100 *active* patients, excluding patients who have been enrolled then withdrawn for various reasons such as starting an additional blood thinner, patient preference, etc.). To ensure that we have data on 100 active patients that complete their 1 month visit, we will plan to accrue up to 150 patients. The primary safety end point will be showing noninferiority of clopidogrel monotherapy in reducing ischemic events stratified by presence or absence of *CYP2C19* LOF allele (QuantStudio with Chemagic DNA extraction). All patients will receive clopidogrel (600 mg load & 75 mg maintenance) and aspirin (324 mg load & 81 mg maintenance) for the first week. Those with *CYP2C19* 2* or 3* LOF allele (*CYP2C19* LOF carriers) will be prescribed prasugrel or ticagrelor [prasugrel 60 mg load, maintenance 10 mg or 5 mg (for patients \geq 75 years or $<$ 60 kg) daily or ticagrelor 180 mg load, maintenance 90 mg twice daily (dose escalation with bolus will occur regardless of the timing of the last clopidogrel dose)]. Non-carriers (or those with inconclusive results) will continue with clopidogrel 75 mg daily maintenance dose. Aspirin will be stopped in all patients once *CYP2C19* results are available.

Specific Aim 2: Among participants enrolled in aim 1, aim 2 will determine the incidence of BARC 3 or 5 bleeding events. Other secondary endpoints are post-dismissal all-cause death, any MI up to 180 days, repeat revascularization, or any other BARC bleeding episodes.

SIGNIFICANCE

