Proposed Strategy to Reduce Ischemic Hazard: Cardiac mortality due to MI dominates in the first week after PCI, and the mortality risk is relatively high for 2 weeks after PCI.¹⁷ The risk of acute or subacute stent thrombosis with current generation stents is low. Utilization of *CYP2C19* genotype-guided prescription of oral P2Y12 inhibitor therapy after PCI may improve that ischemic risk by individualizing antiplatelet therapy according to the *CYP2C19* LOF allele status.^{18, 19} The potential benefit of this precision medicine approach by individualizing antiplatelet therapy may be more relevant early after PCI. In a post hoc analysis from the TAILOR-PCI, 80% risk reduction in ischemic events with genotype-guided oral P2Y12 inhibitor therapy was seen in the first 3 months after PCI.²⁰ High prevalence (50%-70%) of non-carriers of *CYP2C19* allows very early deescalation into clopidogrel monotherapy in most patients with HBR and tailors newer P2Y12 inhibitors with higher bleeding risk only to patients with *CYP2C19* LOF allele. PDB and ischemic PCI data will be actively monitored and entered from same number of controls deemed to have HBR. The central goal of our proposal is to address the unmet need of an effective P2Y12 inhibitor protocol among patients with HBR who undergo PCI to lower their incidence of PDB by leveraging the information from their *CYP2C19* genotype. This will allow individualizing antiplatelet treatment while potentially lowering their bleeding and ischemic hazards.

APPROACH: Methodology – General Methods

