- Design Overview.** For *Aim 1*, up to 150 participants with HBR on DAPT with clopidogrel and aspirin, who have undergone successful PCI will be stratified by the *CYP2C19* LOF allele within one week of DAPT initiation. If present, participants will be given prasugrel or ticagrelor monotherapy, and non-carriers will continue with clopidogrel monotherapy. The primary safety endpoint will be a composite of post-dismissal cardiac death/spontaneous MI <30 days or stent thrombosis <90 days of discharge. For *Aim 2*, the same subjects will undergo post-dismissal assessment for BARC 3 or 5 bleeding, all-cause death, any MI, and/or repeat revascularization up to 180 days. Informed consent followed by genotype assessment will be obtained prior to discharge. Loading dose of clopidogrel (600 mg) will be given to all patients and maintenance dose of 75 mg daily will be given, as indicated. We will allow patients to be given loading dose (324 mg) of aspirin either before or at the time of PCI. The choice of stents, access site and treatment site will be at the discretion of the treating physician (**Figure 1**).
- Clopidogrel and prasugrel/ticagrelor administration.** This study will be single-center, single-arm, open label, first-in-human, and a proof-of-concept, pilot and safety study. All participants in the first week will receive clopidogrel bolus (600 mg) and maintenance (75 mg) and aspirin bolus (324 mg, if not on aspirin) and 81mg maintenance. Participants with HBR who meet the inclusion criteria will be stratified by *CYP2C19* LOF allele. Non-carriers (or those with inconclusive results) will continue with maintenance dose of clopidogrel monotherapy at 75 mg daily. If LOF allele is present, they will be prescribed either prasugrel or ticagrelor monotherapy [prasugrel 60 mg load, maintenance 10 mg daily; ticagrelor 180 mg load, maintenance 90 mg twice daily; dose escalation with bolus regardless of timing of the last clopidogrel dose]. Prasugrel will be the preferred agent except when absolutely contraindicated (history of stroke/transient ischemic attack or active bleeding). Patients ≥ 75 years or < 60 kg will receive prasugrel at a reduced dose of 5 mg daily. If there is

Figure 1: Study Flow Chart

a relative contraindication to prasugrel (as determined by the treating physician), the participant will be given ticagrelor. Maintenance aspirin will be discontinued in both arms once genotype testing has been confirmed. (**Figure 1**).

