 - c) **Subject Accrual Plan:** The recruitment will be drawn from the Earl Wood Cardiac Catheterization Laboratory (>1,500 PCIs/year) and Cardiology inpatient services at St. Mary's Hospital. Day 1 will include screening following successful PCI, bleeding risk calculation (ARC-HBR), enrollment, informed consent, and clinical CYP2C19 assay collection. On day 30, a study coordinator phone call will occur to assess ischemic symptoms, readmission, and bleeding. On day 90, a study coordinator phone call will again assess ischemic symptoms, readmissions, and bleeding. All encounters will include drug education and assurance of compliance.
 - d) **Reassessment:** The study coordinator will make phone calls at one and three months to inquire about ischemic symptoms, readmissions at other hospitals with MI, or any bleeding.
7. **Control Cohort:** A cohort of similar patients will be identified from the Mayo Clinic catheterization laboratory PCI registry to determine rates of ischemic and bleeding events in a cohort of HBR post-PCI patients receiving standard of care DAPT after PCI. These patients will be identified by registry review, and we will utilize ICD diagnosis codes to identify bleeding and ischemic events. Retrospective chart review will verify the clinical situation to ensure the validity of the coded diagnoses (to minimize errors inherent to diagnosis coding). There will be no direct patient contact, and patients who refused registry research participation will be excluded from this study. We aim to obtain the following

data:

A. Events

- Event type (category below); diagnosis codes selected from Mayo Clinic database of ICD codes (<https://intranet.mayo.edu/charlie/quantitative-health-sciences-groups/rochester-epidemiology-project/index-of-possible-codes-for-specific-conditions-diseases/>)
- Date of ischemic/bleeding event
- Bleeding Categories
 - *Hemorrhage, gastrointestinal*
 - *Stroke (hemorrhagic)*
 - *Disease, cerebrovascular (hemorrhagic)*
 - *Hematuria*
- Ischemic Categories
 - *Infarction, myocardial*
 - *Disease, cerebrovascular (TIA, ischemic stroke)*

B. Inclusion

- Successful PCI
- Approx. 1 year date range TBD (n = 1500 patients; targeting contemporary PCI patients within the last 2 years).

C. Exclusion

- Enrolled in CHAMP Trial

D. Demographic/Procedure Info to Capture from PCI Registry

- Age/DOB
- Sex
- Race
- Event type (STEMI, NSTEMI/unstable angina, chronic CAD)
- PCI date
- Hemoglobin at time of PCI

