- Hemoglobin at time of bleeding event (obtain from chart review; not available in registry)
- Creatinine and eGFR at time of PCI
- Use of clopidogrel, prasugrel, ticagrelor
- Use of oral anticoagulant (warfarin, apixaban, rivaroxaban)

Aim 1: Detailed Approach

The objective of aim 1 is to determine if clopidogrel monotherapy following successful PCI is safe among non-carriers of CYP2C19 LOF allele. The hypothesis is that carriers of CYP2C19 LOF genotype are unable to metabolize clopidogrel effectively to an active drug that blocks P2Y12 receptors and inhibit platelet aggregation and are therefore at heightened ischemic risk following PCI. We will reduce bleeding risk by giving clopidogrel monotherapy only to non-carriers. Our approach to test this hypothesis is stratifying HBR patients after successful PCI into those with CYP2C19 LOF allele and those with inconclusive results or who are

| Schedule of Events | Day 0 | Day 1 | Day 2 | Day 3 | Day 4 | Day 5 | Day 6 | Day 7 ± 2 days | Day 30 ± 1 week | Day 90 ± 1 week |
|--|-------|-------|------------|-------|-------|-------|-------|-------------------|--------------------|--------------------|
| Stent Placement | ■ | | | | | | | | | |
| Informed Consent | | ■■■ | | | | | | | | |
| Genotype Test Blood Draw | | ■■■■ | | | | | | | | |
| Study Coordinator Call with Genotype Results & Final Medication Decision | | | ■■■■■ | | | | | | | |
| Stop aspirin and continue clopidogrel or change to prasugrel/ticagrelor | | | ■■■■■■■■■■ | | | | | | | |
| 1 st Study Coordinator Follow Up Call | | | | | | | | ■ | | |
| 2 nd Study Coordinator Follow Up Call | | | | | | | | | ■ | |
| 3 rd Study Coordinator Follow Up Call | | | | | | | | | | ■ |

non-carriers. Within first week of DAPT initiation, non-carriers will receive clopidogrel monotherapy, and prasugrel/ticagrelor will be given to patients with CYP2C19 LOF allele. The *rationale* for this aim is to individualize antiplatelet therapy and to reduce bleeding risk by stratifying P2Y12 pharmacotherapy by the CYP2C19 LOF genotype. Large number (50%-70%) of patients are non-carriers and in them clopidogrel monotherapy would suffice and the remainder will receive prasugrel or ticagrelor thereby lowering bleeding risk, cost, and unique adverse effects related to ticagrelor (e.g., bradycardia, dyspnea) or excess bleeding related to prasugrel. Recruitment should not be a challenge at Mayo Clinic, Rochester where 30% of PCI patients are HBR.

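### The control-cohort lists in General Methods 7 do not select HBR patients on DAPT and omit most of the trial's endpoints

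*Combined protocol and SAP*

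**What the plan says.** The narrative of General Methods 7 promises similar patients from the PCI registry: "a cohort of HBR post-PCI patients receiving standard of care DAPT after PCI". The background section on reducing ischemic hazard adds that data will be "entered from same number of controls deemed to have HBR". Specific Aim 1 sets trial accrual at up to 150 to obtain 100 active patients, so this means roughly 100 to 150 controls.

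Lists A to D then say what will be done:

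- **Inclusion (B):** successful PCI, and "Approx. 1 year date range TBD (n = 1500 patients; targeting contemporary PCI patients within the last 2 years".
- **Exclusion (C):** enrollment in the trial. The narrative adds refusal of registry research.
- **Events (A):** MI; TIA or ischemic stroke; and bleeding that is gastrointestinal, hemorrhagic cerebrovascular, or hematuria; each with an event date. On method, "we will utilize ICD diagnosis codes to identify bleeding and ischemic events", with retrospective chart review to verify the coded diagnoses and no patient contact.
- **Fields (D):** age, sex, race, presentation, PCI date, hemoglobin at PCI and at the bleed, creatinine and eGFR, P2Y12 inhibitor, and oral anticoagulant.

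The trial's endpoints are wider. Design Overview states: "The primary safety endpoint will be a composite of post-dismissal cardiac death/spontaneous MI <30 days or stent thrombosis <90 days of discharge". Specific Aim 2 counts BARC 3 or 5 bleeding and continues: "Other secondary endpoints are post-dismissal all-cause death, any MI up to 180 days, repeat revascularization, or any other BARC bleeding episodes".

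**The concern.** The trial has a single arm. Aim 2 nevertheless hypothesizes less bleeding than with standard-of-care DAPT, and its Expected Outcomes anticipate reduced post-discharge bleeding. The control cohort is the only contemporary DAPT group that the protocol plans to collect, so any such statement will lean on it. No formal test against the controls appears in the public text, but even a descriptive comparison needs the same kind of patient and the same endpoints on both sides. A registry team that follows lists A to D literally would produce event rates for a different population and for different events.

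**Working it through.** **1. What n = 1500 represents.** Inputs: more than 1,500 PCIs a year (General Methods 6c); a date range of about one year (list B); and a site "where 30% of PCI patients are HBR" (Aim 1: Detailed Approach, with the same share in its Preliminary Studies). I take 1,500 a year, the stated lower bound, and treat procedures as patients.

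- All PCI, one year: 1,500 × 1 = 1,500. This reproduces the plan's figure.
- HBR only, one year: 1,500 × 0.30 = 450, leaving 1,050 (70%) who are not HBR.
- HBR only, two years: 2 × 450 = 900.
- Time to collect 1,500 HBR patients: 1,500 / 450 = 3.3 years, beyond the two-year limit in list B.
- Against the same-number plan: 1,500 / 150 = 10 times, or 1,500 / 100 = 15 times.

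So 1500 fits an unrestricted all-PCI cohort. It fits neither a one- or two-year HBR cohort nor a cohort the size of the trial. It may be a screening pool, but the text does not say so.

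**2. Can HBR status be established?** Table 1 has 14 major and 6 minor criteria: 14 + 6 = 20, matching the twenty named in Research Design 1. The list D fields address age, two kidney-function levels, two hemoglobin levels and anticoagulation, which is 6. That leaves 20 − 6 = 14 without a field, among them prior bleeding, platelet count, malignancy and cirrhosis. Chronic warfarin or DOAC use is a trial exclusion, so only 5 of the 6 help to identify trial-comparable controls.

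**3. Can DAPT and the anticoagulant exclusion be applied?** List D names three P2Y12 inhibitors but not aspirin, so DAPT cannot be confirmed. Anticoagulant use is recorded, but no rule removes users. The trial excludes chronic users (General Methods 6b), and Aim 1, Potential Problems, explains that they would confound an evaluation of antiplatelet monotherapy.

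**4. Endpoints side by side.**

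| Trial endpoint | In the control list? |
|---|---|
| Cardiac death (primary) | No |
| Spontaneous MI (primary) | MI, not typed |
| Stent thrombosis (primary) | No |
| BARC 3 or 5 (Aim 2) | Bleeding at certain sites, no grade |
| All-cause death (Aim 2) | No |
| Any MI (Aim 2) | Yes |
| Repeat revascularization (Aim 2) | No |
| Other BARC bleeding (Aim 2) | Bleeding at certain sites, no grade |

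One of three primary components is listed, in untyped form, and one of five Aim 2 endpoints is listed as such. A bleed outside the gastrointestinal, cerebrovascular and urinary sites has no category. TIA and ischemic stroke are listed for controls but are not trial endpoints.

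**5. What the list does support.** PCI date and event date give time from PCI to each listed event. The trial's primary windows run from discharge, and discharge date is not listed. Hemoglobin at PCI and at the bleed, with chart review, allows partial grading of bleeds.

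**The case against.** The best defense is that the narrative governs: it says similar, HBR and DAPT, and the lists are working notes. Anticoagulant users can be dropped with a field already captured, hemoglobin gives some severity information, and Aim 2, Background, says the PCI database routinely collects everything after an intervention. Much of this stands. These are gaps in a list, not proof that the data do not exist, and the list goes to the chart where the registry lacks an item (hemoglobin at the bleed). But the narrative gives chart review the task of verifying coded diagnoses, so an event whose code was never searched would not be found. Availability should not be presumed either: the Table 2 footnote reports MI data as unavailable after 2017.

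Three stronger readings are tempting, and the documents do not support them.

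- **Too few controls.** A reader might apply the background statement "Approximately 15% patients undergoing PCI have HBR" and infer a shortage. That is a general figure. The controls come from the site's registry, where the stated share is 30%. At 450 HBR patients, 1 − 150/450 = 67% could be excluded and 150 would remain.
- **A double standard in adjudication.** General Methods 3 counts only trial events that the blinded committee confirms. The text does not say whether control events go to that committee. That is silence, not contradiction.
- **A known direction of bias.** Non-HBR patients and site-limited codes would tend to lower the control bleeding rate. Retained anticoagulant users would tend to raise it, since the introduction ties oral anticoagulants to more bleeding. The net effect cannot be derived, and no control event rates are given from which to size it.

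**Conclusion.** The point holds, as a conflict between the stated control population and the lists meant to produce it. Followed as written, the lists yield an all-PCI cohort of 1500, about 450 of them HBR. HBR status would be only partly classifiable, DAPT unconfirmed and anticoagulant users retained. The primary composite cannot be built from the listed events, and BARC 3 or 5 can be only partly approximated. No size of bias is claimed.

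The 450 rests on the site's 30% share, which is not shown to use the trial's own HBR threshold. It is also before any DAPT, anticoagulant or other exclusion, for which the documents give no rates. The point should be fixed before abstraction but does not undermine the single-arm data. Confidence is moderate: the public text breaks off mid-sentence in Aim 2, Potential Problems, a supplemental table is not shown, and no statistics section is visible.

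**What to change.** Before abstraction begins:

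1. State whether 1500 is the screening pool, fix the date range, and give one control number that agrees with the same-number plan.
2. Apply the trial's HBR definition to controls and capture the criteria it needs. The sponsor must first reconcile General Methods 6a (ARC-HBR score of at least 4) with Research Design 1 (one major or two minor criteria).
3. Exclude chronic warfarin or DOAC users, using the field already captured.
4. Capture aspirin, and require DAPT at discharge for entry to the control cohort, as the stated population implies.
5. Add death with cause, spontaneous and any MI, stent thrombosis, repeat revascularization, and bleeding at any site with BARC grade from the planned chart review. Use the trial's definitions and its 30-, 90- and 180-day windows, and capture discharge date.
6. State as a limitation that control events are first found by ICD code, without patient contact.

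The cost is protocol wording, a longer abstraction form, and more charts screened, because 14 of the 20 HBR criteria have no field. The cohort shrinks to at most about 450 per 1,500 PCI patients before further exclusions. Differences in how events are found will remain.

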5. **Definitions and Role of Data and Safety Monitoring Board (DSMB):** All deaths will be considered cardiac unless a clear noncardiac cause can be ascertained. Spontaneous MI will be defined according to the fourth universal definition.²¹ Periprocedural MI (< 48 hours post-PCI) will be defined according to the 2013 definition of the Society for Cardiovascular Angiography and Interventions.²² Stent thrombosis will be defined and classified according to the Academic Research Consortium-2 definition.²³ BARC bleeding will be defined as previously reported.²⁴ All endpoints will be independently adjudicated by the clinical event committee. An independent DSMB will oversee the individual and collective safety of the patients in the study during enrollment and follow-up. To provide the steering committee with timely feedback on potential safety issues, the DSMB will review the data 3 times during the trial: (1) When the 25th patient is enrolled, (2) when the 50th patient is enrolled, (3) when the 100th patient is enrolled, and (4) when the 100th actively enrolled patient completes 1-month follow-up.
6. **Subjects**
 - a) **Inclusion Criteria:** Informed consent after successful PCI [no non-fatal MI/stroke/repeat target revascularization/bleeding/acute kidney injury] and academic research consortium-high bleeding risk (ARC-HBR) score ≥ 4 .
 - b) **Exclusion Criteria:** Chronic use of warfarin or direct oral anticoagulant (DOAC), unsuccessful PCI (see above), lesions with angiographic thrombus, prior PCI within 6 months (except for staged PCIs within the same hospitalization or within 7 days of initial PCI, in which case enrollment will occur following the final planned/staged PCI), planned PCI greater than 7 days but less than 6 months following index PCI, planned surgical intervention to treat any cardiac or noncardiac condition within 6 months (excluding transcutaneous valve interventions and pacemakers), high risk lesion/stent characteristics (>50% unprotected left main disease, bifurcation disease requiring 2 stents technique, rotational atherectomy, vein graft, unprotected left main intervention, or history of definite stent thrombosis), women of child-bearing age unless negative pregnancy test is done, life expectancy <1 year, known drug/alcohol dependence, and assessment that the patient will not be compliant with the study protocol.

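### The registry controls are called similar, but most of the trial's exclusions are not applied to them and no adjustment is planned, so a crude comparison with standard DAPT is confounded by patient selection

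*Combined protocol and SAP*

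**What the plan says.** General Methods 7 (Control Cohort) opens: "A cohort of similar patients will be identified from the Mayo Clinic catheterization laboratory PCI registry". It describes them as HBR patients on standard DAPT after PCI. The listed criteria are fewer than that description suggests:

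- Inclusion (7B): successful PCI, and "Approx. 1 year date range TBD (n = 1500 patients; targeting contemporary PCI patients within the last 2 years".
- Exclusion (7C): "Enrolled in CHAMP Trial". The title pages are not in the review copy, so I assume that this is the present trial.
- From the opening paragraph: "There will be no direct patient contact, and patients who refused registry research participation will be excluded from this study".

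The trial's own exclusions (Section 6b) are much longer. They start with chronic warfarin or DOAC use and unsuccessful PCI, go on to "lesions with angiographic thrombus, prior PCI within 6 months", and then cover planned later PCI, planned surgery, left main disease or intervention, two-stent bifurcation, rotational atherectomy, vein graft, earlier definite stent thrombosis, life expectancy under 1 year, substance dependence and expected non-compliance.

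Section 7D lists the fields to be captured for controls. They include age, sex, presentation type, hemoglobin, creatinine and eGFR, P2Y12 inhibitor and oral anticoagulant use. No matching, weighting or adjustment is described.

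**The concern.** The trial is single-arm, but several of its statements are comparative. Aim 1 speaks of noninferiority. The Aim 2 introduction expects less bleeding than with standard DAPT, and the Aim 2 research design looks for an association with fewer bleeding and ischemic events. The registry cohort is the only standard-of-care comparator that the plan describes.

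If participants have passed the Section 6b filter and controls have not, the two groups differ before any treatment difference acts. A gap in event rates could then be credited to early aspirin withdrawal when it reflects who was selected. Anticoagulation is the clearest case. It is a major HBR criterion in Table 1, and the Aim 1 discussion of potential problems says that it was excluded from the trial to avoid confounding. For controls it is only recorded.

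The undated window adds two smaller problems. It can be chosen after trial event rates are known. If it overlaps accrual, taking participants out of the control pool also changes who remains.

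**Working it through.** **Inputs from the documents.** The laboratory performs more than 1,500 PCIs a year (Section 6c). For the site's HBR share: "Recruitment should not be a challenge at Mayo Clinic, Rochester where 30% of PCI patients are HBR" (Aim 1: Detailed Approach). For the general share: "Approximately 15% patients undergoing PCI have HBR" (introduction). Accrual is up to 150. Table 2 gives the site's 30-day death or MI rate in 2017 as 5%. That table is not labelled HBR-only, so 5% is illustrative.

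**1. The plan's own figure.** 1,500 PCIs a year × 1 year = 1,500. The stated n is thus one year of all PCI patients. HBR patients alone would be 1,500 × 0.30 = 450 (or 1,500 × 0.15 = 225). HBR status appears in the opening sentence of Section 7 but not in list 7B. The Significance text (strategy to reduce ischemic hazard) instead describes as many HBR controls as participants.

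**2. Criteria side by side.**

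| Criterion | Trial (6a, 6b) | Controls (7) |
|---|---|---|
| HBR rule | ARC-HBR score of at least 4 | HBR in text, rule not stated |
| Successful PCI | required | required |
| Chronic anticoagulation | excluded | captured only |
| Thrombus, high-risk lesion or stent features | excluded | not listed |
| Recent or planned PCI, planned surgery | excluded (with stated exceptions) | not listed |
| Life expectancy under 1 year | excluded | not listed |
| Expected non-compliance | excluded | not listed |

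**3. Possible size.** Let p be the event rate in all HBR patients of the year, f the share enrolled, r the baseline risk of enrolled relative to non-enrolled patients, and c the rate in the non-enrolled. With no treatment effect, p = f·r·c + (1 − f)·c, so c = p / [1 − f(1 − r)], and the trial rate is r·c. With p = 5%:

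| HBR per year | Enrolled in window | f | r | Controls, nobody removed | Controls, participants removed | Trial |
|---|---|---|---|---|---|---|
| 450 | 150 | 0.33 | 0.5 | 5.0% | 6.0% | 3.0% |
| 450 | 150 | 0.33 | 0.75 | 5.0% | 5.5% | 4.1% |
| 450 | 150 | 0.33 | 1 | 5.0% | 5.0% | 5.0% |
| 450 | 150 | 0.33 | 1.25 | 5.0% | 4.6% | 5.8% |
| 225 | 150 | 0.67 | 0.5 | 5.0% | 7.5% | 3.75% |

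First row: c = 0.05 / (1 − 0.333 × 0.5) = 0.060. The gap is 6.0 − 3.0 = 3.0 points. Of these, 5.0 − 3.0 = 2.0 exist with nobody removed, and removal adds 1.0. The 2.0 points would also arise with a window before enrolment, if that year's HBR patients were alike. If only 75 of the 450 enrolled within the window (f = 0.17), removal multiplies the control rate by 1 / (1 − 0.167 × 0.5) = 1.09 at r = 0.5 and by 1.04 at r = 0.75. Removal dominates only in the last row, where it adds 2.5 of 3.75 points.

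**4. Who remains after full overlap.** 450 − 150 = 300, two thirds of the year's HBR patients. If 50% to 80% of the 450 were eligible (assumption), 225 − 150 = 75 to 360 − 150 = 210 of the 300 (25% to 70%) would be eligible but not enrolled. At 40% eligible it would be 180 − 150 = 30 (10%).

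**5. Event lists.** The control categories in 7A are coded gastrointestinal, intracranial and urinary bleeding, MI, and ischemic cerebrovascular events. Death and stent thrombosis are absent, although cardiac death and stent thrombosis belong to the trial's primary composite and all-cause death to its secondary endpoints. Compared crudely, this lowers the control rate.

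**The case against.** A reader might infer something stronger: that the controls are what is left after the trial has taken the good candidates, so that their event rate is inflated. The reference in Aim 1 to consecutive patients lends this some support. The documents still do not establish it:

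- No enrolment dates are given. Overlap is possible but not shown, and the exclusion of participants may only prevent double counting.
- At the site's 30% figure at least two thirds of a year's HBR patients remain. They may include eligible patients who were never approached, and there are no screening or refusal figures.
- Inflation requires enrolled patients to be at lower risk (r below 1). No value is given. The entry score of at least 4 may be stricter than the general rule of one major or two minor criteria in Research Design 1, which could put participants at higher bleeding risk than controls.
- The shorter control event list works the other way, and since death is not listed, no claim about mortality can be built on it.

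It can also be said that this is a pilot, that Section 7 promises only to determine rates, that no formal test is described, that the words on standard DAPT may already keep out some anticoagulated patients, and that age, hemoglobin and eGFR have an obvious use in identifying HBR.

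These points rule out a claim of known direction and a claim that overlap is the main mechanism. They leave standing that most Section 6b exclusions are not applied, that no adjustment is specified, and that the aims nonetheless speak comparatively.

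**Conclusion.** The point holds as one of comparability. Followed as written, Section 7 yields a cohort that differs from the participants by design, and a crude comparison with it cannot separate treatment from selection. Higher-risk controls are plausible given what Section 6b removes, but the net direction is not determined.

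In the illustration (p = 5%, 450 HBR patients, 150 enrolled, no treatment effect), selection alone gives a gap of 0.9 points at r = 0.75 and 2.0 points at r = 0.5. Full overlap raises these to 1.4 and 3.0. The gap is zero at r = 1 and reverses at r = 1.25. The values of r and full overlap are assumptions. The part present without overlap reflects all selection into the trial. The unapplied exclusions are the component that the plan can control. Participant removal is the smaller part unless the HBR pool is nearer the general 15% figure.

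This should be corrected before the comparison is made. It does not affect the conduct of the single arm.

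**What to change.** 1. Apply to controls, at extraction, the trial's HBR entry criterion and every Section 6b exclusion that the registry or chart can show, including oral anticoagulant use. The score in Section 6a and the major/minor rule in Research Design 1 must first be reconciled into one rule that can be read from the records.
2. State the window's start and end dates relative to first and last enrolment, before trial event rates are known. A window wholly before enrolment makes participant removal irrelevant but gives less contemporary controls. Either choice is defensible if fixed in advance.
3. Report control rates weighted to the trial participants on fields already captured (age, sex, presentation type, hemoglobin, eGFR), beside the crude rates.

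The cost is protocol wording, a standard weighting analysis and extra chart extraction. The extraction goes beyond lesion details, because planned surgery and life expectancy must also be sought. There will be fewer controls than the roughly 450 HBR patients in a year's extract. Refusal, expected non-compliance and other unrecorded factors cannot be weighted away and should be stated as a limitation.
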